### **4.3 Subject Identification**

After having obtained the written informed consent and verified that all eligibility criteria are met, subjects will be included in the study and will be allocated a unique identification number consisting in 6 digits: 2 digits for country identification, 2 digits for site identification and 2 digits (allocated sequentially) for subject identification.

 CONFIDENTIAL	Protocol No. LUF-44-001 Version No. 3.0 Date January 20 th 2017	Page 19 / 43
---	--	--------------

## 5 INVESTIGATIONAL MEDICINAL PRODUCTS

The product investigated is Lipiodol® Ultra Fluid used in association with surgical glues, together referred to as “mixture”.

Lipiodol® Ultra Fluid will be manufactured, labeled, packaged and released in accordance with local applicable requirement.

### 5.1 Lipiodol® Ultra Fluid

Lipiodol® Ultra Fluid (480 mg I/ml) is a solution for injection.

Composition: Ethyl esters of iodized fatty acids of poppy seed oil \* qs ad for one ampoule.

\* Iodine content: 48 %, i.e. 480 mg per ml.

Refer to applicable SmPC.

### 5.2 Packaging, Labeling, Storage

The IMP will consist of one 10 ml type I glass ampoule of Lipiodol® Ultra Fluid packaged in a carton box and labeled as per Indian requirements. It shall be stored according to its applicable SmPC, i.e. protected from light.

Each IMP will be identified with a single ID of 4 digits and labeled with a single use detachable label that will allow ensuring accuracy of IMP allocation per subject.

In case of a second vascular embolization procedure for a single subject, a second IMP will be allocated to the subject.

The participating sites must ensure that ampoules are securely stored in order to avoid misuse.

### 5.3 Condition of Investigational Medicinal Product Administration

Lipiodol® Ultra Fluid will be administered in association with surgical glues.

Commercially available surgical glues will be used by the sites according to the investigator choice and usual practice. Brand name of the surgical glues used and applicable SmPCs will be collected.

Vascular embolization with liquid agents is a complex and delicate technique which should only be performed by trained physicians in an appropriate medicosurgical setting.

A premature polymerisation reaction may exceptionally occur between Lipiodol Ultra Fluid and certain glues or batches of glues. Prior to any use of new batches of Lipiodol® Ultra Fluid or glue, it is mandatory that investigators verify *in vitro* and document the compatibility between the glue used and Lipiodol Ultra-Fluid.

The dose of Lipiodol® Ultra Fluid administered during the embolization procedure depends on lesion size. The Lipiodol® Ultra Fluid and liquid embolizing agent (surgical glue) mixture may vary from 20 to 80% but usually consists of a 50/50 mixture.

The Lipiodol® and surgical glue mixture should be administered via **selective arterial catheterization only**.

Guerbet    CONFIDENTIAL	Protocol No. LUF-44-001 Version No. 3.0 Date January 20 th 2017	Page 20 / 43
--	--	--------------

The volume of Lipiodol® Ultra Fluid injected should not exceed 15 ml during each procedure of vascular embolization.

## **5.4 Investigational Medicinal Product Compliance and Accountability**

The investigator, the hospital pharmacist, or other allowed personnel will keep accurate records of Investigational Medicinal Products accountability at site level as well as accurate records of the batch numbers and IMP(s) given to each subject.

The dosing information will be recorded in individual subject's records. When protocol required IMP administration conditions are not followed, reason(s) will be given and recorded by the investigator.

 CONFIDENTIAL	Protocol No. LUF-44-001 Version No. 3.0 Date January 20 th 2017	Page 21 / 43
---	--	--------------

## 6 CONCOMITANT TREATMENTS

### 6.1 General considerations

Any medication present from 7 days before first vascular embolization or concomitant medication administered during the study will be recorded in the subject Case Report Form (CRF). The following information will be captured:

- Drug (brand name or generic name)
- Route of administration
- Indication
- Purpose (medical history/AE/pre-medication/other)
- Duration of treatment (start and stop period from enrolment and from the IMP administration)

Any contrast media administered during the reporting period should be included.

Anesthetic medication administered for other procedures than the study procedures should not be reported.

### 6.2 Interaction with other medications or contraindications

#### Interleukin II:

The risk of developing a reaction to the contrast agents is increased in the event of previous treatment with interleukin II (IV route): skin rash or, more rarely, hypotension, oliguria, or even renal failure. Please refer to non-inclusion criteria N°7.

#### Anticoagulants:

Interventional radiology and catheter angiogram may be risky in patients taking anticoagulants. Their stop should be evaluated before to decide to enroll the patient. Please refer to non-inclusion criteria N°8.

#### Diuretics:

In the event of dehydration provoked by diuretics, the risk of acute renal failure is increased, especially when high doses of iodinated contrast agents are used. Precautions for use: re-hydration before administration of the iodinated contrast agent.

For the following medications, their stop within two days before embolization procedure should be evaluated before to decide to enroll the patient. Please refer to non-inclusion criteria N° 6:

#### Beta-blockers:

In the event of shock or hypotension due to iodinated contrast agents, beta-blockers reduce the effectiveness of the cardiovascular mechanisms that compensate for blood-pressure disturbances.

Treatment with beta-blockers should be stopped, whenever possible, before the vascular embolization procedure.

#### Metformin:

 CONFIDENTIAL	Protocol No. LUF-44-001 Version No. 3.0 Date January 20 th 2017	Page 22 / 43
---	--	--------------

In diabetic patients, intra-arterial administration of Lipiodol® Ultra Fluid may cause lactic acidosis induced by diminished renal function.

Treatment with metformin must be suspended 48 hours before the investigation and only restarted 2 days after the vascular embolization procedure.

## 7 EVALUATION CRITERIA

### 7.1 Primary Criterion

The primary evaluation criterion is the number and percentage of subjects experiencing adverse drugs reactions (ADRs) occurring during the course of each vascular embolization procedure after administration of Lipiodol® Ultra Fluid in association with surgical glues and before catheterization laboratory discharge.

Adverse events (AEs) will be collected during subject participation to the study, i.e. from written informed consent until end of the follow-up period. Site investigators will be required to assess the causal relationship to the mixture of Lipiodol® Ultra Fluid associated with surgical glues as described in section 10.1.3. All AEs assessed as related to the mixture of Lipiodol® Ultra Fluid and surgical glues will be qualified as ADRs.

### 7.2 Secondary Criteria

The study will evaluate additional safety criteria:

- ADRs from the first administration of Lipiodol® Ultra Fluid in association with surgical glues up to the end of the follow-up period.
- The complete set of AEs collected during the study, regardless of causal relationship assessments, from written informed consent until end of the follow-up period.

Efficacy will be explored with the following assessments:

- Target obliteration per lesion evaluated before the first procedure according to 4 level-score: 1. <50%; 2. 50-75%; 3. 75-99%; and 4. 100% corresponding to a complete nidus obliteration rate
- Post-procedure obliteration per lesion will be evaluated after each procedure according to the same 4 level-obliteration-score
- Successful lesions embolization, expressed as the lesions achieving the targeted percentage of obliteration

At subject enrolment visit, all lesions designated for vascular embolization using Lipiodol® Ultra Fluid associated with surgical glue will be described on the basis of the most recent angiogram and will be associated to a target percent obliteration (i.e. at least x% obliteration or approximately x% obliteration) that is expected to be reached during the procedure. After the procedure, the percent obliteration will be assessed on earliest available angiogram (e.g. Digital Subtraction Angiography (DSA), Computerized Tomography-Angiography (CTA), Magnetic Resonance Angiography (MRA), vascular imaging Ultrasound (US), Doppler US) consistence with the target obliteration will be provided by the investigator.

Guerbet    CONFIDENTIAL	Protocol No. LUF-44-001 Version No. 3.0 Date January 20 th 2017	Page 23 / 43
--	--	--------------

## 8 NUMBER OF SUBJECTS

According to Guerbet best update knowledge of the use of Lipiodol® Ultra Fluid along with glues in embolization procedure no particular safety signal with a related incidence could lead to design a safety study with a specific sample size. No specific hypothesis could be set up and no statistical test planned, therefore number of subjects for the study is based on the requirement of 125 subjects as specified by SEC radio-diagnostic on January 19th 2017. Subjects' data will be analyzed with descriptive statistics investigating in clinical routine the general safety and efficacy of the procedure in an exploratory fashion.

 CONFIDENTIAL	Protocol No. LUF-44-001 Version No. 3.0 Date January 20 th 2017	Page 24 / 43
---	--	--------------

## 9 STUDY SCHEDULE AND PROCEDURES

The study consists in the following procedures:

- Subject enrolment,
- First study procedure (vascular embolization procedure using the mixture Lipiodol® Ultra Fluid associated with surgical glue) that may occur on the same day or within 7 days after the subject enrolment,
- An optional second study procedure if done within 30 days after the first one,
- A safety follow-up within 30 +/- 3 days after the last procedure using Lipiodol® Ultra Fluid associated with surgical glues that could be a visit, a phone call or completed with available medical records.

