### 9.4 Safety follow-up at one month

Collection of data relevant to the safety follow-up of the subject is expected at 30 +/- 3 days after the last procedure using Lipiodol® Ultra Fluid associated with surgical glues

Safety follow-up is expected when at least one administration of the mixture Lipiodol® Ultra Fluid in association with surgical glues will occur.

The following information will be collected by the site:

- Date and kind of follow-up (visit, phone, medical records)
- New therapeutic/palliative procedure if any within the period, administered to the subject for the study disease: Date, type (embolization using other material, surgery, radiosurgery, other) and reason (adverse event, completion of study disease therapeutic/palliative strategy).
- Safety information: adverse event(s), whether serious or not. For more information on safety reporting, refer to Section 10
- Concomitant medications

 CONFIDENTIAL	Protocol No. LUF-44-001 Version No. 3.0 Date January 20 th 2017	Page 26 / 43
---	--	--------------

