#### 10.1.2 Recording/Collection of Adverse Events

The Investigator or his/her designee will invite the subject to report any abnormality experienced as part of the usual clinical follow-up.

All AE, whether considered as related or not to the administration of the mixture of Lipiodol® Ultra Fluid and surgical glues and/or the study procedure of vascular embolization should be reported in the medical file and the CRF and followed up from onset to resolution or stabilization of sequelae. If no follow-up is performed, the investigator must provide a justification.

In order to ensure complete safety data collection, all AEs occurring during the time of the subject's participation in the study, must be reported and followed. As reminder the subject's participation is defined as the period from written informed consent to the last study observation and defined in Section 11.

The following safety information must be collected by the investigator using the same procedure as AEs: medication errors and uses outside what is foreseen in the protocol, including misuse and abuse of the product, suspicion of transmission of an infectious agent via the product, reactions resulting from an occupational exposure, unusual failure in efficacy, overdose (symptomatic or not), all reports of pregnant or breastfeeding women exposure even if uneventful, all reports of suspected drug-drug interaction with another product (symptomatic or not).

In the context of the study, overdose is defined as a total volume of Lipiodol® Ultra Fluid administered of 15mL during a procedure of vascular embolization using Lipiodol® Ultra Fluid in association with surgical glues.

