### 11.2 End of Study Participation for a Subject

End of study participation for a subject should be the end of follow-up for all subjects with at least one administration of mixture of Lipiodol® Ultra Fluid and surgical glue

Criteria for premature discontinuation of subjects:

- Inclusion criteria not met / Non inclusion criteria met
- Adverse Event (according to the investigator's judgement)
- Withdrawal of subject's consent
- Discovery of an unexpected, significant, or unacceptable risk to the subjects enrolled in the study
- At the discretion of the investigator if the subject safety or well-being is not compatible with study continuation
- Cancellation of the scheduled study procedure using Lipiodol® Ultra Fluid associated with surgical glues
- Lost-to-follow-up
- Other reason to be specified

For discontinued subjects, all data available at the time of their premature discontinuation will be reported in the medical file and the CRF (e.g. enrolment data, safety data, administration data if any, reason for discontinuation). The investigator must make every effort to collect and record all follow-up safety information (i.e. adverse events), unless the subject withdraws consent for further data collection for the study.

Discontinued subjects will receive appropriate medical care decided with the treating physicians for their condition.

 CONFIDENTIAL	Protocol No. LUF-44-001 Version No. 3.0 Date January 20 th 2017	Page 33 / 43
---	--	--------------

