### 5.6. Safety Evaluation

All safety analyses will be performed using the TS except otherwise specified.

CONFIDENTIAL	STATISTICAL ANALYSIS PLAN N° LUF-44-001  VERSION N° 2.0	Page 17 / 29
	DATED: JUNE 30, 2021	

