### **5.6.5. Vital signs, physical findings and other observations related to safety**

Data collected at the end of the safety follow-up period (30 days after the last study procedure [30 days]) will be presented:

- Summary statistics (number [n], mean, standard deviation [SD], median, minimum, and maximum) on the time interval (in days) between date of follow-up and date of last study procedure,
- Kind of follow-up (number of subjects and percent [n row / N subjects] \* 100%),

CONFIDENTIAL	STATISTICAL ANALYSIS PLAN N° LUF-44-001  VERSION N° 2.0	Page 21 / 29
--------------	---	--------------

- Number and percentage of subjects undergoing a new therapeutic/palliative procedure for the study disease,
- Summary statistics (number [n], mean, standard deviation [SD], median, minimum, and maximum) on the time interval (in days) between first procedure after last study procedure and last study procedure,
- Reason of procedure (number of subjects and percent [n row / N subjects having a new procedure) \* 100]),
- Type of procedure (number of subjects and percent [n row / N subjects having a new procedure) \* 100]).

Listings on data collected at the end of the safety follow-up period will be presented in CSR appendix 16.2.7

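### The one-month safety follow-up may be completed from medical records without asking the subject, so events that go uncaptured lower the secondary one-month AE and ADR percentages, and no visible table shows by how much

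*Protocol*

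**What the plan says.** After the last study procedure the protocol schedules one safety follow-up, at 30 +/- 3 days. Protocol 9 describes it as one "that could be a visit, a phone call or completed with available medical records". Protocol 9.4 has the site record "Date and kind of follow-up (visit, phone, medical records"), so records are an ordinary option, on a par with the other two, and not a fallback after failed contact.

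On how AEs are found, Protocol 10.1.2 states: "The Investigator or his/her designee will invite the subject to report any abnormality experienced as part of the usual clinical follow-up".

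On the denominator, SAP 5.6 states: "All safety analyses will be performed using the TS except otherwise specified". Protocol 12.1 and SAP 5.2 define that set by at least one injection of the mixture; completed follow-up is not a condition. Protocol 12.5 and SAP 3.5 rule out imputation.

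SAP 5.6.2.4 repeats the ADR and AE analyses for two windows that depend on the follow-up: from the last laboratory discharge to the end of follow-up, and from the first administration to the end of follow-up. SAP 5.6.5 tabulates "Kind of follow-up (number of subjects and percent"), but no AE or ADR table in the visible SAP is split by it.

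**The concern.** Reading a chart invites no one to report anything. Pain, fever or a deficit managed at home, or an admission to another hospital, need not appear in the treating site's records. Such a subject can be closed as followed up with no AE, and the tables then cannot tell a subject who was asked and had nothing from one who was never asked.

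At stake are the one-month AE and ADR percentages, which answer a stated secondary objective in a study registered as a post-authorisation safety study. If events are missed these percentages come out too low, and a reader has no planned output from which to judge by how much.

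**Working it through.** **1. What happens to a subject with no captured event.** The statistic is the percentage of subjects with at least one AE or ADR, built from AE records. SAP 3.1 bases percentages on non-missing recorded categories and Protocol 12.5 refers to available data, but neither rule is worked out for AE incidence. The absence of an AE record is not a missing category. With a Treated Set denominator and no imputation, a treated subject with no AE record is therefore a non-event, whether or not anyone asked. This is an inference from the set and the missing-data rules; no sentence states it. It applies only to subjects with no captured event: a records-only subject with an event in the chart, or a lost subject with an event before loss, counts as having one.

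**2. Which results depend on the follow-up.** The primary criterion (Protocol 7.1; SAP 2.3.1 and 5.6.2.1) closes at catheterization laboratory discharge, before any follow-up mode applies. Only the secondary windows in SAP 5.6.2.4 that run to the end of follow-up are affected.

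**3. Direction and size.** Let p be the true one-month event proportion, d the share lost before any event is captured, f the share followed by records only, and s the share of events in records-only subjects that appear in the records. Assume visit and phone follow-up capture all events, and p is the same in every group. Then

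expected observed proportion = p × [(1 − d − f) + f × s]

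relative bias = −(d + f × (1 − s)), which is never positive.

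The documents give none of p, d, f or s. All values below are assumptions.

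| d | f | s | Bracket | True 10% reads as | True 20% reads as | Relative bias |
|---|---|---|---|---|---|---|
| 0 | 25% | 1 | 0.75 + 0.25 = 1 | 10.0% | 20.0% | 0 |
| 0 | 25% | 0.8 | 0.75 + 0.20 = 0.95 | 9.5% | 19.0% | −5% |
| 5% | 25% | 0.5 | 0.70 + 0.125 = 0.825 | 8.25% | 16.5% | −17.5% |
| 10% | 50% | 0.5 | 0.40 + 0.25 = 0.65 | 6.5% | 13.0% | −35% |

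**4. Effect of the denominator alone.** Suppose 125 treated subjects (the planned number, Protocol 8), 12 lost without a captured event, and 10 of the other 113 with an event. The Treated Set figure is 10/125 = 8.0%. Among those followed it is 10/113 = 8.8%. If all 12 lost subjects had an event it is 22/125 = 17.6%.

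**5. If no event is seen.** The one-sided 95% upper limit is 1 − 0.05^(1/n). It is 2.37% if all 125 are fully ascertained, 3.14% if only 94 are, and 4.72% if only 62 are. The Treated Set denominator implies the first figure whatever the true extent of follow-up.

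The plan has no figure of its own to reproduce here: 125 is a regulatory requirement, with no rate or precision target behind it.

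**The case against.** AE capture does not rest on the day-30 contact alone. All AEs during participation must be reported and followed (Protocol 10.1.2), SAEs go out within 24 hours of occurrence (10.2.2), and a second procedure is a further collection point (9.3). For discontinued subjects "The investigator must make every effort to collect and record all follow-up safety information" (11.2). The sponsor's safety board reviews AEs at least quarterly, and reasons for further procedures are reviewed with under-reporting in mind (3.4, 10.2.1). Mode and timing of follow-up, disposition and discontinuation reasons are tabulated, and all AEs are listed. Flexible follow-up is a deliberate choice in a routine-practice study. The results concerned are descriptive, and sampling error is comparable with most of the illustrated bias: 25 of 125 (20%) has a 95% Clopper-Pearson interval of 13.4% to 28.1%, so of the table's last column but one only 13.0% falls outside.

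Much of this stands. It limits the reach of the point and makes a large bias less certain. But none of these provisions elicits an event from a subject whose follow-up is a chart review, and a marginal table of follow-up mode does not show the event rate within each mode. Nor does a wide interval excuse a systematic error, which the interval does not reflect.

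SAP 5.6.2 counts AEs with missing causality as related to the mixture (unless onset precedes the first procedure). That may push ADR percentages up, so the net direction for ADRs after both effects is not established. It acts only on AEs already reported, however, and does nothing for events never captured.

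Some SAP pages show no text, so the absence of a breakdown by mode is established for the visible SAP only.

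**Conclusion.** The point holds for the secondary one-month AE and ADR percentages. The protocol lets the only scheduled follow-up after the last procedure be done without asking the subject, and the Treated Set denominator turns any resulting under-capture into a lower percentage.

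A reader might infer more, and the documents do not support it. They do not show that the study's safety result as a whole is biased, since the primary criterion closes before follow-up begins. They do not state that records-only or lost subjects count as event-free; that follows only for those with no captured event. And they do not show that the bias is large. Under the assumptions above it runs from nil to a relative −35%; it is nil if records are complete and no one is lost, and its true value cannot be computed from the documents. This is a worthwhile and inexpensive improvement, not a flaw that invalidates the study.

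**What to change.** 1. **Protocol 9 and 9.4.** Require a visit or phone contact with the subject. Let medical records supplement it, or replace it only after documented failed contact attempts. This needs one small additional CRF field for the attempts.
2. **SAP 5.6.2.4.** State the one-month AE/ADR denominator and keep the Treated Set percentage as the main figure. Beside it, report the number of subjects with records-only follow-up and the number with none. Show post-discharge and whole-study AE/ADR counts and percentages by kind of follow-up (visit / phone / records only / none). The mode of follow-up is already collected.
3. **Any supplementary percentage in directly contacted subjects** must keep those who died or had a captured event before the contact; otherwise it drops fatal and early cases and can itself understate risk. It remains descriptive: follow-up mode may depend on outcome, so a difference between modes does not isolate under-capture.
4. **SAP 5.2.** Add follow-up not done to the deviation list, which names a mistimed follow-up visit but has no separate entry for an absent one.

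The cost is a phone call for some subjects, one CRF field, and a few table columns with small cells. The reported one-month rate may be higher. The SAP changes help even if follow-up is already complete.
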